### 14.3 Plasma and Whole Blood Collection for Biomarker Analysis

Plasma Collection: Whole blood will be collected via peripheral venipuncture into EDTA tubes (lavender top) to monitor cytokine and glutamine levels. Samples will be centrifuged and plasma collected and stored at -70°C.

Whole Blood Collection: Whole Blood samples will be collected via peripheral venipuncture into three different blood collection tubes:

1. Blood RNA tubes: to monitor immune gene expression
2. CPT tubes: to monitor immune cell subsets
3. EDTA tube: to monitor T-Cell Receptor (TCR) clonality

All Plasma and Whole Blood Samples will be collected at the time points indicated in the PK and Biomarker Sampling Schedule ([Attachment 2](#)) and will be processed and shipped according to instructions provided in the Laboratory Manual.

The biomarker samples may also be used for the evaluation of additional exploratory biomarkers that are not pre-specified in this protocol based upon new scientific literature and/or preclinical data.

#### **14.4 Biomarker Assessment**

Biomarkers assessed on tumor tissue are designed to measure biological effect of CB-839 in combination with nivolumab to identify potential predictors of response.

Target expression: Tumor glutaminase gene expression profiles will be determined and tumor glutaminase protein will be assessed via immunohistochemistry (IHC)

Target engagement will be assessed by measuring levels of plasma glutamine

The glutaminolytic signature will be measured in the tumor via gene expression and IHC for Myc and p-S6 protein

Immune marker expression and modulation will be assessed in peripheral blood and tumor tissue (cytokines and immune cell populations)

### **15.0 PHARMACOKINETIC EVALUATION**

#### **15.1 Blood Collection**

Plasma PK samples will be used to measure concentrations of CB-839 and its major metabolite 110826. These samples may also be used for exploratory biomarker analyses including, but not limited to, measurements of amino acid levels, enzymes such as glutaminase, glutamine synthetase, pyruvate carboxylase, and arginase. Blood samples for PK analysis should be

collected at the requested time but must be obtained within a 15 min window of the requested time. The exact actual time of collection must be noted in the source documents and eCRFs.

During the Phase 1 Dose Escalation, plasma PK samples will be collected on Cycle 1, Days 1 and 15 at predose and postdose at 0.5, 1, 2, 4, 6, and 8 hr as well as predose on Cycle 2 Day 1 and Cycle 3 Day 1. Patients enrolled on study who start taking PPIs will have plasma PK samples drawn at the same time points indicated above within 2 weeks of starting PPIs. During the Phase 2 Cohort Expansion, plasma PK will be collected for population PK analysis prior to dosing on Cycle 1, Day 1 and Day 15, Cycle 2 Day 1, and Cycle 3 Day 1. Refer to the PK and Biomarker Sampling Schedule ([Attachment 2](#)) for time points and blood volumes to be collected.

## 15.2 Bioanalytical Methodology

The plasma samples will be analyzed for CB-839 and its major metabolite 110826 by using a validated liquid chromatography tandem mass spectrometry (LC-MS/MS) method of appropriate specificity and sensitivity according to Good Laboratory Practices (GLPs).

## 16.0 STATISTICAL ANALYSIS

### 16.1 General Statistical Considerations

Protocol CX-839-004 is a Phase 1/2 multicenter, open-label study in patients with advanced and metastatic or refractory solid tumors.

Since this is an open-label clinical trial, descriptive statistics will be employed to analyze the data by tumor type. Summary statistics for continuous variables will include the mean, standard deviation, median, and range (minimum/maximum). Categorical variables will be presented by tumor type as frequency counts and percentages, and time-to-event variables will be summarized by Kaplan-Meier plots, medians, and ranges.

The data will be tabulated and analyzed with respect to patient enrollment and disposition, demographic and baseline characteristics, prior and concomitant medications, efficacy, and safety measures. The efficacy analysis will be conducted on the Efficacy Evaluable Population as well as on all treated patients. The safety analysis will be performed on the Safety Population.

All confidence intervals will be constructed at the 95% confidence level. Data listings will be created to support each table and to present all data collected.

## 16.2 Independent Radiology Committee (IRC)

An IRC will be established to evaluate tumor scans from patients in Cohort 4 only in a central and independent fashion. The IRC will comprise board-certified radiologists who will determine radiographic responses and progression following study start. Additional imaging results may be requested by the Sponsor for IRC review.

Additional details regarding IRC member qualification, training, methods, procedures, and other issues relevant to committee operations will be described in the IRC Charter.

## 16.3 Sample Size and Power

**Dose Escalation:** The goal is to determine a dose level of CB-839 for which the rate of DLTs is less than 33%. A minimum of 9-12 patients are planned for Dose Escalation.

**Dose Expansion:** For Cohorts 1-6, Simon's two-stage design ([Simon 1989](#)) will be used as outlined in [Table 22.2-1](#) below. The null hypothesis that the response rate is [ p0 ] will be tested against a one-sided alternative. In the first stage, [ n1 ] patients will be accrued. If there are [ r1 ] or fewer responses in these [ n1 ] patients, the study will be stopped. Otherwise, [ n - n1 ] additional patients will be accrued for a total of [ n ]. The null hypothesis will be rejected if [ r2 + 1 ] or more responses are observed in [ n ] patients. This design yields a type I error rate of 0.1 and power of 80% when the true response rate is [ p1 ].

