**Table 22.2-1: Summary of Sample Size and Power for Expansion Cohorts**

Cohort	p0 (Background ORR (%))	p1 (Target ORR (%))	A	Power (%)	n1 for Stage 1 (r1)	n2 (n - n1) for Stage 2	Total n (r2)
1	25%	40%	0.1	80	25 (7)	27	52 (16)
2	5%	15%	0.1	80	20 (1)	36	56 (4)
3	5%	20%	0.1	80	9 (0)	15	24 (2)
4	5%	20%	0.1	80	9 (0)**	66	75 (13)
5	5%	15%	0.1	80	20 (1)	36	56 (4)
6	5%	20%	0.1	80	9 (0)	15	24 (2)

\*For all cohorts, false positive rate ( $\alpha$ ) = 0.1

\*\*Completed prior to protocol Amendment 2 expansion of cohort

## Expanded Cohort 4

A multi-stage design will be used as a guide for the melanoma expansion cohort 4 to decide whether the treatment of CB-839 in combination with nivolumab warrants more extensive development in this population. At first, a Simon 2-stage design (Table 22.2-1) with a reasonable false positive rate (eg, FPR < 10%) and false negative rate (eg, FNR < 20%) was used for the decision making based on assumptions of target (20%) and background (5%) response rate. Following a positive result in the initial two stage design and preliminary evidence of a treatment effect that may represent substantial improvement over available therapies, approximately 75 subjects in total will be treated in Cohort 4. The sample size at this expanded stage is determined based on the ability to produce a confidence interval that would exclude the historic response rate (assumed to be 10%) and to provide sufficient information for a reliable understanding of the safety profile. Specifically, the lower limit of the 95% CI associated with observation of an objective response rate of 18.7% in 75 treated subjects (14/75 responders) excludes 10%. Interim clinical monitoring will be performed in this expansion to ensure adequate safety and tolerability as well as favorable risk/benefit by assessing preliminary efficacy measures such as objective response rate and duration of response.

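### Cohort 4 is listed with alpha 0.1 and 80% power for 5% versus 20%, but its 14-of-75 rule has about 60% power and a type I error of 0.0016% at 5% (1.4% at 10%)

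*Protocol*

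**What the plan says.** Protocol section 16.3 opens the expansion paragraph with "For Cohorts 1-6, Simon's two-stage design". It says the null response rate "will be tested against a one-sided alternative" and sets out the two rules:

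- Stage 1: "If there are [ r1 ] or fewer responses in these [ n1 ] patients, the study will be stopped".
- Final: "The null hypothesis will be rejected if [ r2 + 1 ] or more responses are observed in [ n ] patients".

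It then gives the operating characteristics for all of these cohorts: "This design yields a type I error rate of 0.1 and power of 80" per cent at the target rate p1.

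In Table 22.2-1 the Cohort 4 row reads p0 5%, p1 20%, alpha 0.1, power 80, n1 = 9 (r1 = 0), n2 = 66, n = 75 (r2 = 13). A table footnote begins "For all cohorts, false positive rate" and sets that rate at 0.1. A second footnote, attached to the 9 (0) entry, says only that this part was completed before Amendment 2.

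The Expanded Cohort 4 text under the table gives a different basis for the 75 patients. They are meant to yield a confidence interval that "would exclude the historic response rate (assumed to be 10" per cent), and 14 responses in 75 is given as the result that does so. Section 6.3.2.4 attributes 5% versus 20%, alpha 0.1 and 80% power to the original design with 24 patients (9, then 15 more, at least 3 responses).

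SAP section 5.3 carries the same sentence (there for Cohorts 1-5, so Cohort 4 is included). SAP Table 1 has the same row and footnotes, and the same expansion text follows it.

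**The concern.** The row combines two designs. The sample size and cutoff were updated for the expansion, while p0, p1, alpha and power stayed as they were for 24 patients. A cutoff chosen so that a two-sided 95% interval excludes 10% cannot also be a one-sided 10%-level test of 5%. Neither document gives a type I error or power for the rule that will be used.

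Cohort 4 is the largest cohort and the only one enlarged because of observed activity. Its result is meant to guide whether the combination goes on to more extensive development. Someone relying on the table would take a result short of 14 responses, for example 11 to 13 in 75, as a negative outcome of a design with only a 20% chance of missing the target rate. The actual chance is higher, so such a result says less against the combination than the table implies.

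**Working it through.** **Inputs.** All come from Table 22.2-1 and section 16.3: n1 = 9, r1 = 0, n = 75, r2 = 13, p0 = 5%, p1 = 20%. The 10% background rate is from the Expanded Cohort 4 text. The 24-patient design (9 (0), 24 (2)) and the interim count of 3 responders in 16 evaluable patients are from section 6.3.2.4. The Clopper-Pearson method is from SAP section 7.4.1.

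**Formula.** With X1 ~ Bin(n1, p) and X2 ~ Bin(n − n1, p), the exact probability of rejecting is

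P(reject | p) = Σ over x = r1+1, …, n1 of P(X1 = x) × P(X2 ≥ r2 + 1 − x).

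At p0 this is the type I error; at p1 it is the power.

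**Step 1: reproduce the plan's other figures.**

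| Row | Design | Type I error at p0 | Power at p1 |
|---|---|---|---|
| Cohort 1 | 25 (7), 52 (16) | 0.099 | 80.0% |
| Cohorts 2 and 5 | 20 (1), 56 (4) | 0.097 | 80.1% |
| Cohorts 3 and 6, and original Cohort 4 | 9 (0), 24 (2) | 0.093 | 80.5% |

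The formula matches every other row, and the 0.1 and 80% in the Cohort 4 row match the 24-patient design.

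**Step 2: the rule as listed for Cohort 4 (at least 1 in 9, then at least 14 in 75).**

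| Basis | Type I error at 5% | Type I error at 10% | Power at 20% |
|---|---|---|---|
| Two-stage, as listed | 0.0016% | 1.4% | 59.8% |
| At least 14 in 75, no Stage 1 stop | 0.0019% | 1.6% | 65.9% |
| At least 1/9, then 3/24, then 14/75 | 0.0015% | 1.3% | 58.0% |
| Stated | 10% | not given | 80% |

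**Step 3: power at 20% with Stage 1 already passed.**

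- Probability of stopping at Stage 1: 0.8^9 = 13.4%.
- Given that Stage 1 was passed: 0.598 / (1 − 0.134) = 69.1%.
- Given 3 responders in the first 16, 11 more are needed in the remaining 75 − 16 = 59: P(Bin(59, 0.2) ≥ 11) = 65.4%.

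The chance of missing the criterion at a true 20% is therefore 40.2% (two-stage), 34.1% (no stop), 34.6% (given 3/16) or 30.9% (given Stage 1 passed).

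**Step 4: where 80% power is reached.** It needs a true rate of about 22% without the Stage 1 stop and just over 23% with it.

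**Step 5: the confidence-interval statement.** The Clopper-Pearson 95% interval for 14/75 is 10.6% to 29.3%; for 13/75 the lower limit is 9.6%. So 14 is indeed the smallest count in 75 that excludes 10%, and that statement is correct.

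**Step 6: the counts just below the cutoff.** Under Bin(75, 0.2), 11 to 13 responses occur with probability of about 25%. With the same Stage 1 stop, a cutoff of 11 in 75 would have a type I error of 10.2% at 10% and power of 80.1% at 20%. That shows how far the 14-response cutoff lies from the error rates printed beside it.

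**The case against.** The best defence is that the plan largely explains itself. The text directly below the table says the Simon design at 5% versus 20% was used first, and that the 75-patient stage was sized on an interval excluding 10%. Section 6.3.2.4 assigns alpha 0.1 and 80% power to the 24-patient design. The expansion design is described as a guide, section 16.1 calls for descriptive statistics, and the SAP reports the response rate with a Clopper-Pearson interval whatever the table says. The rule is stricter than stated, so false positives are not inflated. And 59.8% counts trials stopped at 0 of 9, which can no longer happen.

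Much of this is fair. The prose does give the true origin of 14/75 and of the 10% rate. The first footnote covers alpha only; the 80% comes from the row and the sentence in section 16.3. The 59.8% is the literal two-stage figure, and 65% to 69% better describes the expansion from where it stood at Amendment 2. How a result of 11 to 13 responses would be read is a judgement.

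None of it rescues the stated figures. The explanatory text does not withdraw alpha 0.1 or 80% power for the 75-patient rule and offers no replacement. The Stage 1 footnote does not say they have lapsed. The most favourable basis gives 69.1%.

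**Conclusion.** The concern holds. The protocol and the SAP both attach a type I error of 0.1 and 80% power to a Cohort 4 rule that has neither. The rule's type I error is 0.0016% at the tabulated 5% and 1.4% at 10% (1.6% without the Stage 1 stop). Its power at 20% is 59.8% as listed and 65% to 69% with Stage 1 set aside or passed. The tabulated p0 of 5% also conflicts with the 10% on which the cutoff rests.

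The error makes the design look more powerful than it is; it does not raise the risk of a false claim of activity. The figures are exact binomial and assume exactly 75 patients in the denominator. The value conditional on 3 of 16 also assumes that those patients are among the 75 and that their responses stand under the primary assessment.

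**What to change.** In protocol Table 22.2-1 and SAP Table 1:

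- Show 9 (0), 24 (2) with 5% versus 20%, alpha 0.1 and 80% power as the completed initial Cohort 4 design.
- Add a separate row for the expansion: n = 75, success at 14 or more responses, p0 10%, with its type I error and power on one labelled basis. Including the Stage 1 stop, these are 1.4%, and 59.8% at 20%, with 80% reached at just over 23%. For the 75-patient rule alone, they are 1.6%, and 65.9% at 20%, with 80% reached at about 22%. The other set can go in a footnote, but one row should not mix the two.
- Exclude the expanded Cohort 4 from the alpha and power sentence in protocol section 16.3 and SAP section 5.3, and from the all-cohorts alpha footnote in both tables.

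The cost is a table row, a sentence and a footnote in each document, and a less favourable stated power. Sample size, success criterion, analysis and patient treatment stay as they are.

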**Table 22.2-1: Summary of Sample Size and Power for Expansion Cohorts**

Cohort	p0 (Background ORR (%))	p1 (Target ORR (%))	A	Power (%)	n1 for Stage 1 (r1)	n2 (n - n1) for Stage 2	Total n (r2)
1	25%	40%	0.1	80	25 (7)	27	52 (16)
2	5%	15%	0.1	80	20 (1)	36	56 (4)
3	5%	20%	0.1	80	9 (0)	15	24 (2)
4	5%	20%	0.1	80	9 (0)**	66	75 (13)
5	5%	15%	0.1	80	20 (1)	36	56 (4)
6	5%	20%	0.1	80	9 (0)	15	24 (2)

\*For all cohorts, false positive rate ( $\alpha$ ) = 0.1

\*\*Completed prior to protocol Amendment 2 expansion of cohort

## Expanded Cohort 4

A multi-stage design will be used as a guide for the melanoma expansion cohort 4 to decide whether the treatment of CB-839 in combination with nivolumab warrants more extensive development in this population. At first, a Simon 2-stage design (Table 22.2-1) with a reasonable false positive rate (eg, FPR < 10%) and false negative rate (eg, FNR < 20%) was used for the decision making based on assumptions of target (20%) and background (5%) response rate. Following a positive result in the initial two stage design and preliminary evidence of a treatment effect that may represent substantial improvement over available therapies, approximately 75 subjects in total will be treated in Cohort 4. The sample size at this expanded stage is determined based on the ability to produce a confidence interval that would exclude the historic response rate (assumed to be 10%) and to provide sufficient information for a reliable understanding of the safety profile. Specifically, the lower limit of the 95% CI associated with observation of an objective response rate of 18.7% in 75 treated subjects (14/75 responders) excludes 10%. Interim clinical monitoring will be performed in this expansion to ensure adequate safety and tolerability as well as favorable risk/benefit by assessing preliminary efficacy measures such as objective response rate and duration of response.

## 16.4 Analysis Populations

### 16.4.1 Safety Population

All patients who receive at least 1 dose of CB-839 or nivolumab will be included in the analysis of safety, regardless of the duration of treatment.

AE and laboratory data from all patients in the safety population will be evaluated for safety. Patients from dose escalation will be combined with patients from cohort expansion for safety evaluation; all safety evaluation will be evaluated *by tumor type*. Data will be tabulated to examine the frequency, organ systems affected, and relationship to study drugs. No formal interim analysis is planned; however, safety data will be examined on an ongoing basis to ensure safety of the study patients and compliance with the trial dose escalation and expansion rules.

### 16.4.2 DLT-evaluable Populations in Dose Escalation

DLTs will be evaluated during dose escalation. Unless doses are missed in Cycle 1 due to DLT(s), a patient must receive at least 75% of the planned CB-839 doses (43 of 56 total doses) to be considered evaluable for DLT. If a patient received less than 43 doses of CB-839 in the first 28 days of treatment for reasons other than a DLT, the patient will be considered non-evaluable for DLT and replaced. Patients must receive both doses of nivolumab in Cycle 1 in order to be evaluable for DLT.

Patients who discontinue the study prior to receiving the requisite study treatment administrations for reasons that include, but are not limited to, clinical/radiographic progression, voluntary withdrawal, or complications that the Principal Investigator considers secondary to the patient's malignancy will not be considered evaluable for DLT and will be replaced.

### 16.4.3 Response Evaluable Population

Patients treated in the protocol expansion phase or at the RP2D in the escalation phase who have measurable disease at baseline and complete at least one post-baseline tumor assessment, or discontinue study medication early due to study drug-related toxicity, or experience clinical disease progression will be considered evaluable for RECIST 1.1 response evaluation. Patients who discontinue study due to early disease-related death will be included in the response evaluable population if they received at least 21 days of treatment (approximately 42 doses of CB-839 and 2 doses of nivolumab). Patients who do not meet the aforementioned requirements will be considered non-evaluable for response and will be replaced.

#### 16.4.3.1 Melanoma Confirmed PD Population

In addition to the above criteria, melanoma patients who have confirmation of PD > 4 weeks after the initial date of PD in the immediate prior line of treatment will be included in the Confirmed PD population.

## 16.5 Efficacy Analysis

For the primary efficacy analysis, response to treatment will be evaluated by RECIST v1.1. For all cohorts except for Cohort 4, the primary endpoint will be investigator-assessed, while for Cohort 4 the primary endpoint will be IRC assessed.

The Kaplan-Meier method will be used to estimate the median Duration of Response (DOR), Progression-Free Survival (PFS), and overall survival (OS) for each treatment cohort in Dose Expansion.

- ORR is defined as the percentage of patients with complete response (CR) or partial response (PR) according to the RECIST 1.1 criteria. Response confirmation is required a minimum of 4 weeks after the date of the initial determination of response.
- DOR is defined as the number of days from the date of initial response (PR or better) to the date of first documented disease progression/relapse or death, whichever occurs first.
- PFS is defined as the number of days from the date of treatment initiation (i.e., C1D1) to the date of documented disease progression (radiographic or clinical) or death from any cause, whichever occurs first, and will be calculated for all patients who receive at least one dose of study treatment. In the event that no disease progression or death is documented prior to study termination, analysis cutoff, or the start of confounding anticancer therapy, these endpoints will be censored at the date of last available tumor assessment.
- OS is defined as the number of days from the date of treatment initiation (i.e., Cycle 1 Day 1) to the date of death from any cause and will be calculated for all patients who receive at least one dose of treatment. In the event that no death is documented prior to study termination or analysis cutoff, OS will be censored at the last date the patient is known to be alive.

## 16.6 Safety Analysis

Safety variables to be analyzed by tumor type are AEs, laboratory test results (hematology, coagulation, serum chemistry, and urinalysis), ECG, weight, and vital signs.

Adverse event terms recorded on the eCRFs will be mapped to preferred terms using the most recent version of the Medical Dictionary for Drug Regulatory Activities (MedDRA®). All AEs will be summarized according to the system organ class and preferred term within the organ class. Adverse events will be tallied for overall frequency (number and percentage of patients), worst reported severity, and relationship to study drug for each preferred term per patient. Serious adverse events will be similarly summarized. Listings of deaths, SAEs, and AEs leading to early termination of study treatment or premature withdrawal from study will also be provided.

Laboratory variables will be examined using mean change in value from baseline to scheduled time points. The baseline value of a variable is defined as the last value obtained on or before the date and time of the first dose of CB-839 or nivolumab.

ECG, weight, and vital signs will also be summarized by changes from baseline to scheduled time points using descriptive statistics.

## 16.7 Pharmacokinetic Analysis

For Phase 1- Dose Escalation PK samples, a noncompartmental method of analysis will be used to analyze the plasma concentrations of CB-839.  $C_{max}$  and the time to attain the  $C_{max}$  ( $T_{max}$ ) will be determined directly from the observed data. A partial AUC ( $AUC_{0-8}$ ) will be calculated on Days 1 and 15 in Cycle 1. For Phase 2- Cohort Expansion, plasma samples will be collected to perform population PK analysis.

